2.4 Derivation of Response Status and Non-Responder Imputation

For each 'complete' dataset, the imputed post-baseline values will be rounded to the same precision as the observed data. Response status (e.g., PPASI 75 at each visit) will be determined accordingly.

The imputed response status for missing due to reasons other than COVID-19 will be overridden by non-responder imputation (Section 2.1) to ensure that multiple imputation is only applied to missing due to COVID-19:

- Using NRI approach, all missing due to reasons other than COVID-19 will be categorized as non-responders. In addition, subjects whose change/percent change from Baseline cannot be calculated because of a missing Baseline will be considered as a non-responder at all post-baseline visits, unless the post-baseline value is zero.
- The only exception is that a subject will be categorized as a responder for the visit if the subject is a responder both before and after an SAP-specified visit window in the particular Study Period.

2.5 Analysis

The statistical analysis will use the Cochran-Mantel-Haenszel (CMH) test adjusted by the actual stratification factors (Baseline BSA category and Baseline ppIGA category).

2.5.1 Analysis of Each Dataset

For each of the K 'complete' datasets, the CMH test will be used to estimate the treatment difference versus placebo and the corresponding standard error.

2.5.2 Synthesis of Results for Statistical Inference

The results from the K 'complete' datasets will be synthesized using the SAS procedure PROC MIANALYZE, following Rubin's formula (Rubin, 1987⁵), to derive the MI estimator of the treatment difference for the final inferences.

Rubin's formula

We fit the analysis model to the kth 'complete' dataset, denoting the estimate of the treatment difference q by $\tilde{\theta}_k$ from the kth 'complete' dataset, and denoting the corresponding estimate of the variance as V_k .

The MI estimator of q (point estimator obtained from PROC MIANALYZE), $\tilde{\theta}_{MI}$, is the average of the K individual estimators:

$$\tilde{\theta}_{MI} = \frac{1}{K} \sum_{k=1}^K \tilde{\theta}_k.$$

The estimated variance of $\tilde{\theta}_{MI}$, is a combination of the between- and within-imputation variability as follows:

$$V_{MI} = W + \left(1 + \frac{1}{K}\right)B$$

Where $W = \frac{1}{K} \sum_{k=1}^K V_k$ is the within-imputation variability and $B = \frac{1}{K-1} \sum_{k=1}^K (\tilde{\theta}_k - \tilde{\theta}_{MI})^2$

is the between-imputation variance.

It has been shown⁵ that the statistic

$$T = \frac{\tilde{\theta}_{MI} - \theta}{\sqrt{V_{MI}}}$$

has an approximate t_v distribution where $v=(K-1)[(1+W/B)]^2$. Statistical inference, including hypothesis testing and confidence intervals for the treatment effect, will be based on this T-statistic.

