2.4 Sample Size Determination

The ppIGA is an endpoint that has been used in another clinical trial in the palmoplantar psoriasis population and which is based on the modified Investigator's Global Assessment version of 2011.^{1,2} Given the lack of historical ppIGA data from risankizumab trials, the assumption of response rates in the current study are based on the relevant endpoints of PPASI 75 and PPASI 90 from risankizumab PsO Studies M15-992, M15-995, and M16-008, among subjects who had Baseline PPASI of at least 8. Among these subjects, approximately 80% and 75% of subjects from the risankizumab (RZB) group achieved PPASI 75 and PPASI 90, respectively; compared to 50% and 40% in the placebo (PBO) group.

Assuming that 75% of subjects from the RZB group and 45% of subjects from the PBO group would achieve the primary endpoint of ppIGA of 0 or 1 with at least a 2-point reduction from Baseline at Week 16, the sample size of 168 subjects (84 subjects per group) will provide more than 90% power to detect the treatment difference between RZB and PBO, under a 2-sided significance level of 0.05.

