9.0 Efficacy Analyses

9.1 General Considerations

All efficacy analyses will be conducted among the ITT Population. All statistical tests will be performed at a 2-sided alpha level of 0.05.

The Primary Analysis will be conducted after all continuing subjects complete Week 16 and all data pertaining to Period A are cleaned. This will be the only and final analysis for efficacy in Period A. Study sites and subjects will remain blinded to their initial treatment assignment for the duration of the entire study.

For categorical endpoints, comparisons will be made between risankizumab and placebo using the Cochran-Mantel-Haenszel (CMH) test, adjusting for the actual values of stratification factors (Baseline ppIGA and Baseline BSA categories). In case of any stratum with zero subject in either treatment group, no stratification factor will be controlled. Non-responder imputation (NRI) incorporating multiple imputation (MI) to handle missing data due to COVID-19 (NRI-C) will be the primary approach to handle missing values.

For continuous endpoints, comparisons will be made between risankizumab and placebo based on the fixed term of treatment from a Mixed-effect Model Repeat Measurement (MMRM) model including the Baseline value and observed measurements at all post-baseline visits, adjusting for the fixed effects of treatment, actual values of stratification factors, visit and treatment-by-visit interaction as covariates. The MMRM will be the primary approach to handle missing values.

"Baseline" refers to the last non-missing observation on or before the date of the first administration of study drug or the date of randomization if no study drug is administered. For variables where the assessment time is collected on the ePRO device, the baseline measurement must be prior to the time of the first administration of study drug.

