9.3.2 Main Analysis of Primary Efficacy Endpoint

The following null hypothesis corresponding to the primary endpoint will be tested under a two-sided significance level of 0.05:

- There is no difference between risankizumab and placebo, with respect to the proportion of subjects achieving ppIGA of 0 or 1 with at least a 2-point reduction from Baseline at Week 16.

The primary endpoint will be analyzed among the ITT Population, using the Cochran-Mantel-Haenszel (CMH) test adjusting for the actual values of stratification factors.

The attributes of the estimand corresponding to the primary efficacy endpoint are summarized in Table 2.

Table 2. Summary of the Estimand Attributes of the Primary Efficacy Endpoint

Estimand Label	Attributes of the Estimand				
	Treatment	Endpoint	Population	Handling of Intercurrent Events	Statistical Summary
ppIGA 0 or 1 at Week 16	Risankizumab 150 mg / Placebo	Achievement of ppIGA 0 or 1 with a least 2-point reduction from Baseline at Week 16	ITT	Subjects who discontinued study drug due to lack of efficacy prior to Week 16 will be considered as non-responders.	Difference in proportion of subjects achieving ppIGA 0 or 1 with a least 2-point reduction from Baseline at Week 16 between risankizumab 150 mg and placebo

Comparison will be made between risankizumab and placebo using the CMH test, adjusting for the actual values of stratification factors (Baseline ppIGA and Baseline BSA categories). NRI-C will be the primary approach to handle missing data.

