9.6 Efficacy Subgroup Analyses

To evaluate the consistency of the efficacy over demographic and other baseline disease characteristics, the primary efficacy endpoint will be analyzed in selected subgroups as follows:

- Age group (< 40 years, ≥ 40)
- Sex (male, female)
- Race (white, non-white)

- Smoking (current, ex- or never)
- Body mass index (BMI) (normal: < 25, overweight: ≥ 25 to < 30, obese: ≥ 30)
- Baseline ppIGA ("moderate" [3], "severe" [4])
- Baseline BSA (< 10% versus ≥ 10%);
- Psoriatic arthritis (yes, no)
- Body weight (≤ 100 kg, > 100 kg)

Of note, if the BMI ≥ 30 subgroup have fewer than 10% of the total subjects, it will be combined with its adjacent subgroup.

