MODEL *//*OVERRIDE MISSING VALUES NOT DUE TO COVID-19 WITH TRADITIONAL
NRI*/
DATA ALLF; SET ALL;
  /*COVID19_XX='Y' IF MISSING AT WEEK XX IS DUE TO COVID-19; IF NOT,
OVERRIDE WITH TRADITIONAL NRI*/
  /*VARIABLE PPASI75NRI_XX: TRADITIONAL NRI DATA AT WEEK XX, WHICH
COVERS THE SPECIAL HANDLING SUCH AS THE BEFORE-AND-AFTER EXCEPTION IN
THE PARTICULAR STUDY PERIOD*/
  IF COVID19_16 NE 'Y' THEN PPASI75_16= PPASI75NRI_16;
RUN;
PROC SORT DATA=ALLF; BY _IMPUTATION_ SUBJID; RUN;

/*****
/*ANALYSIS MODEL*/
/*****

```

```
/*KEY CODE: ANALYZING EACH 'COMPLETE' DATASET*/  
/*****/  
/*INDIVIDUAL-LEVEL DATA --> # OF RESPONDERS & # OF SUBJECTS, TO BE READ-  
IN TO PROC STDRADE*/  
PROC FREQ DATA=ALL;  
  BY _IMPUTATION_;  
  TABLES TRT01PN*STRATAN* PPASI75_16/LIST NOCUM NOPRINT OUT=COUNT_TABLE;  
  /*WEEK 16 RESULTS AS AN EXAMPLE*/  
RUN;  
DATA COUNT_TABLE; SET COUNT_TABLE;  
  DROP PERCENT;  
RUN;  
PROC TRANSPOSE DATA=COUNT_TABLE OUT=FREQ_TABLE PREFIX=RESP;  
ID PPASI75_16;  
BY _IMPUTATION_ TRT01PN STRATAN;  
VAR COUNT;  
RUN;  
DATA FREQ_TABLE1; SET FREQ_TABLE;  
  CASE=RESP1;  
  SIZE=SUM(RESP0, RESP1);  
  KEEP _IMPUTATION_ TRT01PN STRATAN CASE SIZE;  
RUN;  
  
/*RE-ORDER TO SET 1 (PLACEBO) AS THE REFERENCE GROUP*/  
DATA FREQ_TABLE2; SET FREQ_TABLE1;  
  IF TRT01PN=2 THEN TRT01PN=0;  
RUN;  
  
/*CALCULATE THE COMMON RISK DIFF FOR EACH COMPLETE DATASET*/  
PROC STDRADE DATA=FREQ_TABLE2  
  METHOD=MH STAT=RISK EFFECT=DIFF;  
  BY _IMPUTATION_;  
  POPULATION GROUP=TRT01PN EVENT=CASE TOTAL=SIZE;  
  STRATA STRATAN / ORDER=DATA STATS(CL=NONE) EFFECT;  
  ODS OUTPUT EFFECT=EFFECT;  
RUN;  
  
/*COMBINING RESULTS USING PROC MIANALYZE*/  
/*****/  
PROC MIANALYZE DATA=EFFECT;  
  ODS OUTPUT PARAMETERESTIMATES=RISK_DIFF_MH;  
  MODELEFFECTS RiskDiff;  
  STDERR StdErr;  
RUN;
```

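### The plan names the stratified CMH test, but SAP Appendix E tests a Wald-type T on the Mantel-Haenszel risk difference: slightly liberal overall, more clearly so in small stratified subgroups

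*SAP*

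**What the plan says.** SAP 9.3.2 states the primary test: "The primary endpoint will be analyzed among the ITT Population, using the Cochran-Mantel-Haenszel (CMH) test adjusting for the actual values of stratification factors". SAP 9.1 sets the level: "All statistical tests will be performed at a 2-sided alpha level of 0.05". Protocol 7.4 names the same test, SAP 9.4.2 applies it to the ranked secondary endpoints, and Appendix E 2.5 repeats it for the NRI-C analysis, which is the primary missing-data approach for all of these endpoints.

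The operative detail is in Appendix E. For each completed dataset, "the CMH test will be used to estimate the treatment difference versus placebo and the corresponding standard error". The sample code gets these two quantities from PROC STDRATE with "METHOD=MH STAT=RISK EFFECT=DIFF" and passes them to PROC MIANALYZE. Section 2.5.2 forms T, the pooled difference over the square root of its Rubin variance, and adds: "Statistical inference, including hypothesis testing and confidence intervals for the treatment effect, will be based on this T-statistic".

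For subgroups, SAP 9.6 says that "the primary efficacy endpoint will be analyzed in selected subgroups as follows" and lists nine factors. It gives no separate method for small groups beyond merging a BMI class of 30 or more that holds under 10% of subjects. SAP 9.1 removes all stratification when a stratum has no subject in one arm.

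**The concern.** A CMH test and a ratio of the MH difference to its standard error are different tests. CMH uses the variance that holds under the null with the margins fixed. The ratio is a Wald test that uses a variance estimated at the observed rates. A programmer following SAP 9.3.2 and one following Appendix E can report different p-values from the same data, and for a borderline ranked endpoint that could change the decision. The difference also has a direction. A per-stratum binomial variance is too small when the arm-by-stratum cells are small, so the Wald test rejects too often and its interval is too short. With four strata (two ppIGA levels by two BSA levels), cells become small quickly in subgroups.

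**Working it through.** **Inputs.** Two-sided 0.05 (SAP 9.1). Rates of 75% and 45%, with 84 per arm (SAP 2.4). 1:1 allocation and four strata (SAP 2.3). K = 30 imputations (Appendix E 2.3). Not in the documents, and therefore assumed: strata shares, subgroup sizes, block size 4, the COVID-missing fraction, and the standard-error formula behind the MH difference.

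**The plan's own figure.** SAP 2.4 claims that "the sample size of 168 subjects (84 subjects per group) will provide more than 90% power to detect the treatment difference". The mean rate is 0.60. The null SE is √(2·0.60·0.40/84) = 0.0756. The alternative SE is √((0.75·0.25 + 0.45·0.55)/84) = 0.0720. Then (0.30 − 1.96·0.0756)/0.0720 = 2.11, which gives power of 98.3%. The claim is reproduced.

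**What each test uses.** In stratum h, let a and b be the responders among n1 and n0 subjects, N = n1 + n0, m = a + b and w = n1·n0/N.

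- Numerator: w(a/n1 − b/n0) = (a·n0 − b·n1)/N = a − n1·m/N. The MH difference and the CMH statistic therefore share the numerator Σ(a − n1·m/N).
- CMH variance of that sum: Σ n1·n0·m(N − m)/[N²(N − 1)].
- Wald variance of that sum, per-stratum binomial form: Σ w²[p1(1 − p1)/n1 + p0(1 − p0)/n0].

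Only the denominators differ. With nothing imputed, the between-imputation variance is zero and T is the Wald ratio, still not CMH.

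**Why the Wald form is liberal.** The expected value of p̂(1 − p̂) is p(1 − p)(n − 1)/n. With equal strata, 84 per arm is 21 per cell. The factor is 20/21 = 0.952, and the SE shrinks by √0.952 = 0.976. The effective critical value is 1.96·0.976 = 1.913, and the two-sided tail beyond it is 5.6%. At 42 subjects a cell holds about 42/8 = 5.25, so the factor is 4.25/5.25 = 0.81. A cell of one subject contributes zero variance.

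**Simulation.** 200,000 trials per setting (the 60-subject row comes from the same exercise), four equal strata, nothing imputed, SAP 9.1 empty-stratum rule applied. Rejection is at a common rate of 45%; coverage is at 75% versus 45%.

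| Total N | T rejects | CMH rejects | T coverage | Sato rejects | Sato coverage |
|---|---|---|---|---|---|
| 168 | 5.6% | 5.3% | 94.2% | 5.3% | 94.7% |
| 84 | 6.9% | 5.0% | 93.1% | 5.9% | 94.2% |
| 60 | 7.9% | 4.9% | 92.0% | not run | not run |
| 42 | 9.7% | 4.9% | 89.9% | 6.8% | 92.8% |
| 34 | 11.3% | 4.9% | 88.4% | 7.5% | 92.2% |
| 25 | 13.8% | 4.7% | 85.6% | 8.6% | 90.9% |

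Variations:

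- Full trial over null rates of 10-75% and several strata mixes: T 5.4-5.9%, CMH 4.9-5.3%, T coverage 94.1-94.6%.
- Full trial with 2-10% COVID-missing data and K = 30: T 5.6-6.0%, coverage 93.9-94.5%.
- 17 per arm with cells of 6/6/3/2: T 10.3%, CMH 5.5%, coverage 90%. With Sato, 6.3% rejection.
- Two strata only, as in the ppIGA and BSA subgroups: T 6.2% at 84 subjects and 7.5% at 42.
- Unstratified: T 6.4% at 42 and 7.6% at 25. Coverage at 75% versus 45% is 93.3% and 92.0%.
- Power at 84 per arm: 98.4% for T, 98.2% for CMH.

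**The case against.** The strongest reply is that nothing is undefined. Protocol 7.4 leaves the NRI-C details to the SAP, Appendix E sets them out in full, and the estimand is a difference in proportions, which a stratified risk difference pooled by Rubin's rules targets directly. This stands in part: T is prespecified. It does not make T the named test.

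Second, a reader might infer that 5% control of the primary test is lost or that the primary result is in doubt. The documents do not support that. The excess is about half a point, and with the Sato variance (5.2-5.3%) it nearly disappears. At the rates in SAP 2.4, power is about 98% under either test.

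Third, the size depends on a formula that the SAP does not print. This stands. At 17 per arm, the choice between binomial and Sato changes the rejection rate from about 10% to 6.3%.

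Fourth, one can push further, to 8 per arm with cells fixed at 3/2/2/1, and obtain about 21% rejection. That scenario should not be used. Under random allocation, a stratum is often empty in one arm at that size, and the SAP 9.1 rule then drops the stratification.

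Fifth, SAP 9.6 describes a consistency check outside the testing hierarchy and does not itself call for four strata or a p-value. This stands, so the subgroup harm is misleadingly narrow intervals, not a type I error claim. Four strata follow only by carrying SAP 9.1 over, and cannot arise in the ppIGA or BSA subgroups.

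**Conclusion.** The point holds. The plan names the stratified CMH test in several places and specifies a Wald-type T where the analysis is defined; the two should be reconciled. In the confirmatory analyses T is slightly liberal: about 5.4-5.9% against 4.9-5.3%, with CI coverage of about 94-94.5%, power unchanged, and no threat to the primary conclusion at the assumed 30-point effect. In subgroups with four strata the effect is clearer: about 7-8% rejection and 92-93% coverage at 60-84 subjects, and about 10-11% and 88-90% at 34-42. These figures assume the per-stratum binomial standard error. With Sato the excess shrinks to 5.2-5.3% overall and about 6-7.5% at 34-42 subjects, but does not vanish. Subgroup sizes and strata mixes are assumptions throughout. The change should be made because it is cheap and removes an ambiguity about the confirmatory p-value.

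**What to change.** In Appendix E 2.5, keep the MH difference as the estimate in each dataset. For the p-value, use as V_k the CMH null variance on the difference scale: Σ n1·n0·m(N − m)/[N²(N − 1)], divided by (Σw)². Pool by the existing Rubin formula. Because the numerators coincide, T² equals the ordinary CMH chi-square (no continuity correction) when nothing is imputed. The CMH sizes quoted above are for complete data; the pooled version was not simulated with imputed values.

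Wilson-Hilferty pooling of the chi-square should not be described as returning the ordinary CMH p-value. At 1 df and chi-square 3.8415 it gives z = (3.8415^(1/3) − 7/9)/√(2/9) = 1.672, so p = 0.0472 rather than 0.0500.

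Name the Sato variance for the CI of the MH difference. In SAP 9.6, specify a score-type CI, or an unstratified one, when subgroup strata are small, and say what counts as small. Sato alone still covers only about 93% at 42 subjects and 91% at 25. An unstratified Wald interval also falls short, so score-type is the better choice.

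The cost is SAP wording and a few lines of code. The p-value becomes very slightly less favourable, and the test and CI can occasionally disagree at the margin; the SAP should say that the test decides. If the sponsor prefers T, the alternative is to name it as the primary test in SAP 9.1 and 9.3.2 and print its variance.

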3.0 Sample SAS Code

```

/*****/
/*IMPUTATION ALGORITHM*/
/*****/
/*NOTE: THIS APPROACH REQUIRES NO MISSING IN CATEGORICAL COVARIATES AND
REQUIRES AT LEAST ONE OBSERVATION IN BASELIBE OR ONE OF THE POST-
BASELINE VISIT*/

/*PRE-AUGMENTATION - CREATE DUMMY FOR CATEGORICAL VARIABLES*/
/*****/
DATA PPASI_2; SET PPASI;
  /*THE MCMC STATEMENT BELOW ASSUMES MULTI-VARIATE NORMAL*/
  IF TRT01PN=1 THEN TRT1=1; ELSE TRT1=0;
  /*BASELINE BSA and BASELINE PPIGA CATEGORY*/
  IF BSAGR1N = 1 THEN REG1 = 1 ;ELSE REG1 = 0;
  IF PPIGAGR1N = 1 THEN REG2 = 1 ;ELSE REG2 = 0;

RUN;

/*AUGMENTATION STEP -- TO HAVE 30 MONOTONE MISSING DATASETS*/
PROC MI DATA= PPASI_2 OUT= PPASI_MONO NIMPUTE=30 SEED= 21423 /*RANDOM
SEED PRE-DEFINED*/
  ROUND=. . . 0.1 0.1 0.1 /*VALUE ROUND TO 1ST DECIMAL*/
  MIN=. . . 0 0 0 /*MINIMUM VALUE OF PPASI IS 0*/
  MAX=. . . 72 72 72 /*MAXIMUM VALUE OF PPASI IS 72*/
MCMC IMPUTE=MONOTONE ;
/*NOTE: CATEGORICAL VARIABLES SUCH AS TRT1 TRT2 ARE DUMMY, CREATED
ABOVE*/
/*NOTE: ALL OTHER NON-DUMMIED COVARIATES MUST BE CONTINUOUS*/
/*SUPPOSE STRATAN (NUMERIC VARIABLE FOR STRATA) HAS ONLY 2 LEVELS, NO
NEED TO CREATE DUMMY*/
VAR TRT1 BSABL REG2 BASE WK4 WK16;
/*CAUTION TO USE THE "BY" STATEMENT IN MCMC: */
/*MVN MODEL IS FITTED WITHIN EACH 'BY' GROUP, INSTEAD OF ACROSS ALL
GROUPS*/
RUN;

/*IMPUTATION STEP - DETERMINE IMPUTATION DISTRIBUTION AND RANDOMLY
IMPUTE MISSING VALUE TO GENERATE 'COMPLETE' DATASETS*/
/*****/

```

```

PROC MI DATA= PPASI_MONO OUT= PPASI_FULL NIMPUTE=1 SEED= 21931 /*RANDOM
SEED PRE-DEFINED*/
  ROUND= . . . 0.1 0.1 0.1 /*VALUE ROUND TO 1ST DECIMAL*/
  MIN=. . . 0 0 0 /*MINIMUM VALUE OF PPASI IS 0*/
  MAX=. . . 72 72 72 /*MAXIMUM VALUE OF PPASI IS 72*/
  MINMAXITER=1000;
  /*CLASS CATEGORICAL VARIABLES TRT1 AND REG2*/
  CLASS TRT1 REG2;
  VAR TRT1 BSABL REG2 BASE WK4 WK16;
  MONOTONE REG (WK4 WK16); /* IMPUTED SEQUENTIALLY, FROM WK 4 TO 16,
WITH COVARIATES CONSTRUCTED FROM THE CORRESPONDING PRECEDING VARIABLES*/
  BY _IMPUTATION_ ; /*FOR EACH OF THE 30 MONOTONE
MISSING DATASETS, IMPUTE A 'COMPLETE' DATASET*/
RUN;

/*DETERMINE DICHOTOMOUS RESPONSE STATUS, PPASI 75 AT WEEK 16*/
DATA ALL; SET PPASI_FULL;
  IF 0<=WK16<=0.25*BASE THEN PPASI75_16=1;
  ELSE PPASI75_16=0;
RUN;

/*****
*/
/*          DATA HANDLING STEPS TO MERGE COVID-19 STATUS OMITTED
*/
/*          PLACE TO ADD DATA HANDLING AND MERGING STEPS
*/
/*****
*/

/*FOR MI, SKIP THE FOLLOWING CODE, PROCEED TO THE CODE AFTER ANALYSIS
MODEL *//*OVERRIDE MISSING VALUES NOT DUE TO COVID-19 WITH TRADITIONAL
NRI*/
DATA ALLF; SET ALL;
  /*COVID19_XX='Y' IF MISSING AT WEEK XX IS DUE TO COVID-19; IF NOT,
OVERRIDE WITH TRADITIONAL NRI*/
  /*VARIABLE PPASI75NRI_XX: TRADITIONAL NRI DATA AT WEEK XX, WHICH
COVERS THE SPECIAL HANDLING SUCH AS THE BEFORE-AND-AFTER EXCEPTION IN
THE PARTICULAR STUDY PERIOD*/
  IF COVID19_16 NE 'Y' THEN PPASI75_16= PPASI75NRI_16;
RUN;
PROC SORT DATA=ALLF; BY _IMPUTATION_ SUBJID; RUN;

/*****
/*ANALYSIS MODEL*/
/*****

```

```
/*KEY CODE: ANALYZING EACH 'COMPLETE' DATASET*/  
/*****/  
/*INDIVIDUAL-LEVEL DATA --> # OF RESPONDERS & # OF SUBJECTS, TO BE READ-  
IN TO PROC STDRADE*/  
PROC FREQ DATA=ALL;  
  BY _IMPUTATION_;  
  TABLES TRT01PN*STRATAN* PPASI75_16/LIST NOCUM NOPRINT OUT=COUNT_TABLE;  
  /*WEEK 16 RESULTS AS AN EXAMPLE*/  
RUN;  
DATA COUNT_TABLE; SET COUNT_TABLE;  
  DROP PERCENT;  
RUN;  
PROC TRANSPOSE DATA=COUNT_TABLE OUT=FREQ_TABLE PREFIX=RESP;  
ID PPASI75_16;  
BY _IMPUTATION_ TRT01PN STRATAN;  
VAR COUNT;  
RUN;  
DATA FREQ_TABLE1; SET FREQ_TABLE;  
  CASE=RESP1;  
  SIZE=SUM(RESP0, RESP1);  
  KEEP _IMPUTATION_ TRT01PN STRATAN CASE SIZE;  
RUN;  
  
/*RE-ORDER TO SET 1 (PLACEBO) AS THE REFERENCE GROUP*/  
DATA FREQ_TABLE2; SET FREQ_TABLE1;  
  IF TRT01PN=2 THEN TRT01PN=0;  
RUN;  
  
/*CALCULATE THE COMMON RISK DIFF FOR EACH COMPLETE DATASET*/  
PROC STDRADE DATA=FREQ_TABLE2  
  METHOD=MH STAT=RISK EFFECT=DIFF;  
  BY _IMPUTATION_;  
  POPULATION GROUP=TRT01PN EVENT=CASE TOTAL=SIZE;  
  STRATA STRATAN / ORDER=DATA STATS(CL=NONE) EFFECT;  
  ODS OUTPUT EFFECT=EFFECT;  
RUN;  
  
/*COMBINING RESULTS USING PROC MIANALYZE*/  
/*****/  
PROC MIANALYZE DATA=EFFECT;  
  ODS OUTPUT PARAMETERESTIMATES=RISK_DIFF_MH;  
  MODELEFFECTS RiskDiff;  
  STDERR StdErr;  
RUN;
```

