2.2 Study Design Overview

This is a Phase 3b, multicenter, randomized, double-blind, parallel group, placebo-controlled study to evaluate the safety and efficacy of risankizumab (150 mg) compared to placebo in adult subjects with moderate to severe plaque psoriasis with palmoplantar involvement.

The study is comprised of a Screening period of up to 35 days, a 52-week treatment period, and a follow up phone call for safety.

[figure not shown]
The 52-week treatment period includes Period A and Period B.

- Period A, Double-Blind Period (Baseline to Week 16): Eligible subjects will be centrally randomized at the Baseline visit in a 1:1 ratio to receive either risankizumab 150 mg as a single subcutaneous (SC) injection, or matching placebo. Study drug administration will occur at Baseline and Week 4. The final efficacy evaluation of Period A will be at Week 16.
- Period B, Open-Label Period (Week 16 to Week 52): Starting at Week 16, all subjects will receive open label risankizumab 150 mg once every 12 weeks at Weeks 16, 28, and 40. The final efficacy evaluation of Period B will take place at Week 52.

A follow-up phone call for safety will be conducted approximately 20 weeks after administration of the last dose of risankizumab (e.g., Week 60).

The schematic of the study is shown in [Figure 1](#).

Figure 1. Study Schematic

Solid arrows indicate administration of study drug at study visits.

Wk = week.

The Primary Analysis will be performed after the last ongoing subject completing the Week 16 visit or permanently discontinuing the placebo-controlled period, and the data up to Week 16 cutoff date have been cleaned.

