2.0 Non-responder Imputation Incorporating Multiple Imputation (NRI)

2.1 Overall Description of the Method

For a dichotomized outcome variable with missing data, the NRI will categorize any subject who does not have evaluation during a pre-specified visit window as a non-responder for the visit, with two exceptions:

- If the subject is a responder both before and after the pre-specified visit window in the particular Study Period, the subject will be categorized as a responder for the visit.
- If the reason for missing (e.g., missed visits, incomplete visit, out-of-schedule visits, or discontinuations of study drug) is due to COVID-19, the information will be captured in the database and the subject's response status will be imputed using multiple imputation.

Subjects whose change/percent change from Baseline cannot be calculated because of a missing Baseline will be considered as a non-responder at all post-baseline visits, unless the post-baseline value is zero.

Non-responder imputation incorporating multiple imputation (NRI) for missing due to COVID-19 will be implemented as follows.

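### The SAP Appendix E sample code writes the non-responder override to `ALLF` but analyses `ALL`, so the printed NRI-C branch returns the MI-branch result

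*SAP*

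**What the plan says.** The SAP text is consistent on the method. Section 9.2.1 makes NRI-C the primary approach for categorical endpoints: MI only where the cause of missingness is COVID-19, otherwise non-response, apart from a before-and-after exception. Section 9.4.2 applies NRI-C to the ranked secondary endpoints, which include PPASI 75. Section 9.3.2 does the same for the primary ppIGA endpoint: "NRI-C will be the primary approach to handle missing data". Appendix E 2.4 requires imputed status to be overridden wherever the cause is not COVID-19, "to ensure that multiple imputation is only applied to missing due to COVID-19". Full MI is planned only as a sensitivity analysis of the primary endpoint (9.2.1, 9.3.3).

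Appendix E 3.0 illustrates this with sample code for PPASI 75 at Week 16. A comment splits the two uses: "FOR MI, SKIP THE FOLLOWING CODE, PROCEED TO THE CODE AFTER ANALYSIS". The block that MI users skip states its purpose as "OVERRIDE MISSING VALUES NOT DUE TO COVID-19 WITH TRADITIONAL" NRI. It creates `ALLF` from `ALL` and applies "IF COVID19_16 NE 'Y' THEN PPASI75_16= PPASI75NRI_16". The analysis block used by both branches then opens with "PROC FREQ DATA=ALL".

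**The concern.** The override is the only printed step that separates NRI-C from MI. If its output is never analysed, the two branches cannot differ. A programmer who followed the block, or adapted it to another responder endpoint without changing the dataset name, would report under the NRI-C label a result in which every missing value keeps its imputed status.

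The slip would probably be silent, because `ALL` comes from an imputation run by imputation number and should pass through the frequency step without a sort error. If the template were reused for ppIGA, the MI sensitivity analysis would largely repeat the primary analysis, and their agreement would say little about robustness to missing data.

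**Working it through.** **Dataset trace, in the printed order**

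| Step | Reads | Writes |
|---|---|---|
| Derive PPASI 75 status | `PPASI_FULL` | `ALL` |
| COVID-19 merge (stated as omitted) | – | – |
| NRI override (skipped for MI) | `ALL` | `ALLF` |
| Sort | `ALLF` | `ALLF` |
| Frequency counts (both branches) | `ALL` | `COUNT_TABLE` |
| Transpose, risk difference, pooling | `COUNT_TABLE` onward | final estimate |

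`ALLF` is not named after the sort, and no printed step copies it back to `ALL`. The omitted merge comes before `ALLF` exists, so it cannot carry the override into the analysis. Both branches therefore pass the same data to the final steps and return the same estimate, standard error and p-value.

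**The plan's own power figure (background only)**

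SAP 2.4 gives n = 84 per group, 75% v 45%, two-sided 0.05. The pooled normal approximation is

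z = (|p1 − p0|√n − 1.96√(2p̄q̄)) / √(p1q1 + p0q0) = (0.30 × 9.165 − 1.96 × 0.693) / 0.660 = 2.11.

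This is 98.3% power, which agrees with the stated figure of more than 90%.

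**Shift per missing subject**

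A Week 16 value missing for a non-COVID reason counts as 0 under NRI-C and, on average, as the imputed response rate q under `ALL`. With 84 per arm, ignoring strata, one such subject moves that arm's rate by 100 × q/84 points. In the idealised case q equals the historical PPASI 75 rates in SAP 2.4:

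- Risankizumab: 80/84 = 0.95 points, which raises the `ALL` difference.
- Placebo: 50/84 = 0.60 points, which lowers it.
- One in each arm: (80 − 50)/84 = 0.36 points net.

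**Assumed missing fractions, same idealised case**

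The documents project no rate of non-COVID missingness, so these levels are assumptions. The NRI-C difference is 80(1 − m1) − 50(1 − m0), where m1 and m0 are the missing fractions on risankizumab and placebo. `ALL` gives about 30.0 throughout.

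| Missing, risankizumab / placebo | NRI-C difference | `ALL` minus NRI-C |
|---|---|---|
| 2% / 2% | 29.4 | +0.6 |
| 5% / 5% | 28.5 | +1.5 |
| 10% / 10% | 27.0 | +3.0 |
| 5% / 0% | 26.0 | +4.0 |
| 0% / 5% | 32.5 | −2.5 |

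**A less ideal imputation**

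Appendix E imputes PPASI itself by normal regression, bounded at 0 to 72. A toy simulation of this used 84 per arm, 30 imputations, 400 replicates, an assumed PPASI distribution and an assumed 3% COVID-19 missingness:

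| Non-COVID missing per arm | `ALL` | `ALLF` | Shift, points |
|---|---|---|---|
| 0% | 0.299 | 0.299 | 0 |
| 5% | 0.290 | 0.283 | 0.7 |
| 10% | 0.278 | 0.264 | 1.4 |
| 15% | 0.269 | 0.251 | 1.8 |

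At 5% the arm rates were 0.768 v 0.750 (risankizumab) and 0.478 v 0.467 (placebo). The implied imputed response rates are 0.018/0.05 = 36% and 0.011/0.05 = 22%, well below 80% and 50%. The per-subject shifts become 36/84 = 0.43 and 22/84 = 0.26 points. In this toy model Week 4 carried no information on a subject's own Week 16 response; a better predictor would move the result towards the idealised case.

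**Power**

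At the historical 80% v 50%, the same formula gives 98.7% with complete data. Under NRI-C it gives 97.3% at 5% missing per arm and 95.1% at 10%.

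**The case against.** The strongest reply is that the text already fixes the method and that the block is an unadapted template nobody could run verbatim. Much of this stands. The merge is omitted, and `STRATAN`, `COVID19_16` and `PPASI75NRI_16` are used but never created. A comment supposes two strata levels where the trial stratifies on two binary factors. Read as SAS dates, the printed seeds 21423 and 21931 fall in August 2018 and January 2020, before Protocol Version 1.0 of 11 December 2020. A programmer must rewrite the block, and `ALL` is the right input for the MI branch. None of this makes the printed NRI-C branch correct. Section 9.2.1 sends readers to Appendix E for detail, and a dataset name can survive a rewrite.

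Some stronger readings do not hold:

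- A reader might infer that the code contradicts 9.3.2 directly. It is written for PPASI 75, so 9.3.2 is affected only if the template is reused for ppIGA.
- A reader might equate `ALL` with the SAP's own MI analysis. That analysis also forces non-response for assessments missing after discontinuation for lack of efficacy, and no printed step does so.
- A reader might say that the before-and-after exception can never apply at Week 16. It needs a response on both sides: "If the subject is a responder both before and after the pre-specified visit window in the particular Study Period". SAP 2.2 says "The final efficacy evaluation of Period A will be at Week 16", so a later Period A observation is unlikely. The SAP prints no window limits, however, so it cannot be excluded.

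**Conclusion.** The point holds as a minor error in sample code. As printed, the NRI-C branch gives the code's MI-branch result, contrary to SAP 9.2.1, 9.4.2 and Appendix E 2.4.

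A reader might infer that the trial's analysis was run wrongly. The documents do not show this: the production program cannot be seen and the governing text is correct. There is no effect if programmers follow the text, or if no Week 16 data are missing for non-COVID reasons. One side matter is open: if `PPASI75NRI_16` also carries the lack-of-efficacy rule, which the code comment does not say, reading `ALL` would lose that too.

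The shifts of 0.95 and 0.60 points per missing subject are idealised. They assume that imputation reproduces the historical 80% and 50%, which are not the planning rates for this trial (75% v 45% for ppIGA). Bounded-normal imputation of skewed PPASI would probably give smaller shifts; the toy simulation gave about half. A reader might also infer that the slip always favours risankizumab. It does not: the direction depends on which arm has more missing data. Power is little affected, so the estimate is what would mainly move.

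**What to change.** In Appendix E 3.0, use `DATA=ALLF` in the frequency step for the NRI-C branch and keep `DATA=ALL` for the MI branch only. Add a sentence that the SAP text governs over the sample code. Check that the production program follows Appendix E 2.4 for PPASI 75 and for every other responder endpoint built from the template.

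The cost is one dataset name, one sentence and a program check. No protocol amendment or new data are needed.
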